3.2 Trial Endpoint

Both eyes will be assessed at all study visits. The study eye, the eye with the higher, summed fluorescein corneal staining score (type+extent/surface area+depth) at baseline, will be selected for all efficacy analyses. If both eyes score equally, the right eye will be chosen by default as the study eye.

3.2.1 Primary Efficacy Endpoints

The primary efficacy endpoints will include comparison between groups in change from baseline at Day 90 in the following:

- Lissamine green staining scores
- Frequency of stickiness scores as rated on a 0–3 scale (0=never, 1=sometimes, 2=often, 3=constantly)

3.2.2 Secondary Efficacy Endpoints

Exploratory secondary efficacy endpoints will include between-group comparison in change from baseline and proportion of subjects for the following:

- Central corneal clearing defined as a score of 0 in stain intensity in area 1 (area 1=central cornea, defined as central 5 mm of the cornea) at all time points in corneal fluorescein staining
- Total score of 0 in stain intensity in areas 1, 2, 3, and 4 (1 [central]+2 [temporal]+3 [inferior]+4 [nasal]=0) at all time points in corneal fluorescein staining
- Summed score of 0 (type+extent/surface area+depth=0) at all time points in corneal fluorescein staining
- Summed score of 0 (cornea+nasal conjunctiva+temporal conjunctiva = 0) at all time points in corneal and conjunctival lissamine green staining
- Change of ≥ 10 mm in Schirmer test (anesthetized) score at all time points
- Individual and summed symptom frequency score for burning/stinging, itching, grittiness/scratchiness/foreign body sensation, dryness, stickiness, redness of the eye, and tired eye sensation at all time points, rated on a 0-3 scale where 0=never, 1=sometimes, 2=often, and 3=constantly; maximum score=21
- Individual and summed symptom intensity score for burning/stinging, itching, grittiness/scratchiness/foreign body sensation, dryness, stickiness, redness of the eye, and tired eye sensation as measured by the Visual Analogue Scale (VAS), rated on a 0-100 scale where 0=absent and 100=severe

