4.2 Inclusion Criteria

Subjects who meet the following criteria will be included in the study:

1. Subjects ≥ 2 years of age
2. Documented medical history of dry eye disease for a period of at least 6 months
3. Use of artificial tears for at least 3 months prior to screening
4. BCVA better than 20/400 in both eyes
5. Provision of signed, written consent prior to participation in any study-related procedures; or signed written consent from parent or legal guardian if the subject is a minor and signed written assent from minor subject, if appropriate

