4.3 Exclusion Criteria

Subjects who meet any of the following criteria will be excluded from the study:

1. Previous use of CSA 0.05% (Restasis[®]) within the 3 months prior to screening
2. Previous treatment failure on CSA 0.05% (Restasis[®])
3. Current use of systemic cyclosporine
4. Systemic and topical ophthalmic medications that are known to cause dry eye disease are prohibited and must not have been taken within 7 days of screening. These include the following medications:
 - Immunomodulators (permitted if dose is stable for 3 months prior to screening and not expected to change during the study period)
 - General anesthetics
 - Antihistamines (including over-the counter [OTC])
 - Cholinergics
 - Antimuscarinics
 - Tricyclic antidepressants
 - Phenothiazines
5. Any topical ophthalmic medications other than the assigned study medication or the provided artificial tears (Refresh Plus[®])
6. Current active eye disease, other than dry eye disease (ie, any disease for which topical ophthalmic medication is necessary)
7. Abnormal lid position or closure in both eyes
8. End-stage lacrimal disease (Schirmer test score with nasal stimulation of < 3 mm/5 min) or dry eye disease as the result of destruction of conjunctival goblet cells or scarring

9. Presence or anticipated use of punctal occlusion in the study eye
10. Intraocular or refractive surgery (including cataract extraction, LASIK, vitrectomy, or trabeculectomy) in the study eye within 3 months prior to study start
11. Unwilling to discontinue use of contact lenses during the duration of the study
12. Pregnancy or lactation, confirmed by urine pregnancy test. The test will be conducted if the Investigator deems it necessary.
13. Presence or history of any systemic or ocular disorder or condition that could possibly interfere with the interpretation of the study results in the study eye
14. HIV positive or diagnosis of AIDS
15. Known hypersensitivity to any component of the study or procedural medications
16. Participation in any other clinical trial within 30 days prior to screening
17. Unable to reliably report symptoms and history

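### The four score-of-0 proportion endpoints set no baseline condition, so a study eye that was never stained counts as a success

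*Protocol*

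**What the plan says.** Section 3.2.2 of the protocol, repeated in the synopsis, lists four endpoints that are met by a score of zero:

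- central fluorescein: "Central corneal clearing defined as a score of 0 in stain intensity in area 1"
- four corneal areas: "Total score of 0 in stain intensity in areas 1, 2, 3, and 4"
- fluorescein type, extent and depth: "Summed score of 0 (type+extent/surface area+depth=0) at all time points in corneal fluorescein staining"
- lissamine green: "Summed score of 0 (cornea+nasal conjunctiva+temporal conjunctiva = 0) at all time points in corneal and conjunctival lissamine green staining"

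The lead-in in 3.2.2 reads "Exploratory secondary efficacy endpoints will include between-group comparison in change from baseline and proportion of subjects for the following". The synopsis has a similar lead-in without the word exploratory.

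On disease at entry, Section 4.2 asks for "Documented medical history of dry eye disease for a period of at least 6 months", together with artificial tear use, an acuity limit, an age limit and consent. No inclusion or exclusion criterion sets a minimum staining score. Section 3.2 takes as study eye the one with the higher summed fluorescein score at baseline, and the right eye if the two are equal.

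The same list has a Schirmer responder endpoint: "Change of ≥ 10 mm in Schirmer test (anesthetized) score at all time points".

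**The concern.** The word clearing implies that there was staining to clear. As defined, the endpoint is a state at the visit and not a transition from baseline. If some study eyes start at 0 on the measure in question, the reported proportion mixes the baseline prevalence of clean eyes with response to treatment.

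Two things follow. The absolute rate in every arm is too high to be read as a clearing rate, which matters in a pilot whose rates could inform a later trial. The difference between arms is also usually diluted, because clean eyes that stay clean add equally to all arms.

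**Working it through.** **Step 1: can a study eye start at 0?** Taking the rules together:

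- Entry criteria (4.2 and 4.3): no minimum staining on any measure.
- Study-eye rule (3.2): selection is on the summed type, extent and depth score, not on the area 1 grade and not on lissamine green. An eye with only inferior or nasal fluorescein staining can be the study eye with area 1 at 0.
- Ties (3.2): two eyes that both sum to 0 are tied, and the right eye becomes the study eye. So even the summed fluorescein score can be 0, though only when both eyes are 0. That endpoint is better protected than central clearing.
- Grading instructions (6.4.1.2): area 1 is scored for central clearing, with no reference to its baseline grade.

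So such eyes can enter, and if still at 0 they meet the definition. How many there will be is not stated.

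**Step 2: size.** The protocol sections at hand give no rate, effect or power for these endpoints, so there is no figure to reproduce. Inputs from the protocol: about 65 per arm and two-sided alpha 0.05. All other inputs are assumptions:

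- b = share of study eyes at 0 at baseline: 10%, 30% or 50%
- s = share of those still at 0 at the visit: 90% in both arms
- r = true clearing in eyes stained at baseline: 40% active, 15% vehicle

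Proportion as written: p = b·s + (1 − b)·r.

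Power = Φ(d/SE − 1.96), where d is the difference in proportions and SE = √{[p_A(1 − p_A) + p_V(1 − p_V)]/n}. As written, n = 65. Restricted to stained eyes, n = 65(1 − b) and the rates are 40% and 15%.

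Example, b = 50%:

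- Active: 0.45 + 0.5 × 0.40 = 0.650. Vehicle: 0.45 + 0.5 × 0.15 = 0.525. d = 0.125, SE = √[(0.2275 + 0.2494)/65] = 0.0857, power = Φ(1.46 − 1.96) = 31%.
- Restricted: n = 32.5, d = 0.25, SE = √[(0.24 + 0.1275)/32.5] = 0.1063, power = Φ(2.35 − 1.96) = 65%.

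| b | Active v vehicle, as written | Difference (points) | Power as written | Restricted n per arm | Power restricted | Vehicle successes already 0 at baseline |
|---|---|---|---|---|---|---|
| 10% | 45.0% v 22.5% | 22.5 | 80% | 58.5 | 88% | 0.09/0.225 = 40% |
| 30% | 55.0% v 37.5% | 17.5 | 53% | 45.5 | 79% | 0.27/0.375 = 72% |
| 50% | 65.0% v 52.5% | 12.5 | 31% | 32.5 | 65% | 0.45/0.525 = 86% |

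The true difference in stained eyes is 25 points throughout, and the true vehicle clearing rate is 15%.

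**Step 3: sensitivity.**

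- *Drug also protects clean eyes.* With b = 50% and 95% v 80% staying clean, active is 0.475 + 0.200 = 0.675 and vehicle 0.400 + 0.075 = 0.475. Then d = 0.200, SE = 0.0849 and power is 65%, the same as restricted. There is no gain.
- *Smaller effect.* With clearing of 40% v 20%, all clean eyes staying clean, and a pooled-variance power formula, power as written v restricted is 57% v 66%, 36% v 55% and 22% v 42% at 10%, 30% and 50% zeros.
- *Formula.* The pooled-variance formula on the table's inputs gives 78% v 87%, 52% v 77% and 30% v 62%. The pattern is the same.

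**The case against.** - **The share of clean eyes is unknown.** This stands. Choosing the eye with more fluorescein staining makes zeros less likely, and at 10% zeros the loss of power is modest. The definition is still wrong for whatever share occurs.
- **Randomisation balances clean eyes on average.** This also stands. A reader might infer that the rule biases the result towards active drug, or turns a chance baseline imbalance into a false effect. The documents do not support that: allocation is 1:1:1, and chance imbalance is covered by the test's error rate. The harm is inflated rates and, usually, dilution.
- **The proportion of all subjects with a clear cornea is a legitimate quantity.** True, but it is not clearing and should not carry that name.
- **Change from baseline is analysed as well.** An eye that goes from 0 to 0 contributes no change there. This limits the consequence but does not repair the proportions.
- **Section 9.5.3 or an SAP could set the denominator.** The protocol text at hand ends at Section 6.9, so this cannot be excluded. But the success definition is fixed in 3.2.2 and the synopsis, and it would still need to agree with any later rule.
- **Schirmer.** A reader might infer that a fall of 10 mm counts as a success because no direction is given. The ordinary reading of change from baseline is visit minus baseline, so a fall is −10 and fails a threshold of at least 10. Falls count only if an absolute value is read in, and the text has none.

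**Conclusion.** The point holds for the four score-of-0 proportion endpoints. As defined, an eye that was never stained on the measure is a success, and no eligibility or study-eye rule prevents it.

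Under the main assumptions the vehicle rate would read 22.5% to 52.5% where true clearing is 15%. Power would be 80%, 53% and 31%, against 88%, 79% and 65% with a restricted denominator, at 10%, 30% and 50% baseline zeros. These figures illustrate the effect. They rest on assumed rates, model a single endpoint, and shrink or vanish with few baseline zeros or a drug effect in clean eyes.

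Severity is moderate. The endpoints are exploratory secondary endpoints of a pilot, and both primary endpoints are changes from baseline and are unaffected. The Schirmer wording is a matter of clarity only.

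**What to change.** In Section 3.2.2 and the synopsis, define each of the four endpoints as a score of 0 at the visit among study eyes with a baseline score of at least 1 on that same measure. Align Section 9.5.3 and any SAP with this. Keep the change-from-baseline analyses in all subjects. As a clarification, word the Schirmer endpoint as an increase from baseline of at least 10 mm.

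The cost is wording, plus smaller denominators that differ between the four endpoints: about 58, 45 or 32 per arm at 10%, 30% or 50% baseline zeros. Because the restriction uses baseline data only, the comparison remains randomised. No visit, procedure or sample size changes.

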3.2.3 Safety Variables

Safety variables include best-corrected visual acuity (BCVA), slit lamp examination, intraocular pressure (IOP), ophthalmoscopy, and recording of adverse events (AEs). An evaluation of subject comfort and tolerability following the instillation of the first and last dose of medication also will be performed.

3.2.3.1 Subject Comfort and Tolerability

An evaluation of subject comfort and tolerability following the first (Day 0) and last (Day 90) instillations of the study medication will be performed.

3.3 Study Duration and Dates

The duration of study treatment is 90 days, with the primary efficacy assessment at Day 90. Safety and efficacy evaluations will be conducted at Days 14 (± 3 days), 28 (± 3 days), 42 (± 3 days), 60 (± 3 days), and 90 (± 3 days).

4 STUDY POPULATION SELECTION

4.1 Study Population

Male or female subjects ≥ 2 years of age with a diagnosis of dry eye disease will be included in this study. Please see Sections 4.2 and 4.3 for specific inclusion and exclusion criteria, respectively. Approximately 195 evaluable subjects will be enrolled at approximately 20 clinical sites in the United States.

4.2 Inclusion Criteria

Subjects who meet the following criteria will be included in the study:

1. Subjects ≥ 2 years of age
2. Documented medical history of dry eye disease for a period of at least 6 months
3. Use of artificial tears for at least 3 months prior to screening
4. BCVA better than 20/400 in both eyes
5. Provision of signed, written consent prior to participation in any study-related procedures; or signed written consent from parent or legal guardian if the subject is a minor and signed written assent from minor subject, if appropriate

4.3 Exclusion Criteria

Subjects who meet any of the following criteria will be excluded from the study:

1. Previous use of CSA 0.05% (Restasis[®]) within the 3 months prior to screening
2. Previous treatment failure on CSA 0.05% (Restasis[®])
3. Current use of systemic cyclosporine
4. Systemic and topical ophthalmic medications that are known to cause dry eye disease are prohibited and must not have been taken within 7 days of screening. These include the following medications:
 - Immunomodulators (permitted if dose is stable for 3 months prior to screening and not expected to change during the study period)
 - General anesthetics
 - Antihistamines (including over-the counter [OTC])
 - Cholinergics
 - Antimuscarinics
 - Tricyclic antidepressants
 - Phenothiazines
5. Any topical ophthalmic medications other than the assigned study medication or the provided artificial tears (Refresh Plus[®])
6. Current active eye disease, other than dry eye disease (ie, any disease for which topical ophthalmic medication is necessary)
7. Abnormal lid position or closure in both eyes
8. End-stage lacrimal disease (Schirmer test score with nasal stimulation of < 3 mm/5 min) or dry eye disease as the result of destruction of conjunctival goblet cells or scarring

9. Presence or anticipated use of punctal occlusion in the study eye
10. Intraocular or refractive surgery (including cataract extraction, LASIK, vitrectomy, or trabeculectomy) in the study eye within 3 months prior to study start
11. Unwilling to discontinue use of contact lenses during the duration of the study
12. Pregnancy or lactation, confirmed by urine pregnancy test. The test will be conducted if the Investigator deems it necessary.
13. Presence or history of any systemic or ocular disorder or condition that could possibly interfere with the interpretation of the study results in the study eye
14. HIV positive or diagnosis of AIDS
15. Known hypersensitivity to any component of the study or procedural medications
16. Participation in any other clinical trial within 30 days prior to screening
17. Unable to reliably report symptoms and history

5 TRIAL TREATMENT(S)

5.1 Description of Treatments

Treatment with the study drug will be for 90 days, from Day 0 to Day 90 inclusive.

5.1.1 Study Drug

CSA 0.1% and CSA 0.2% will be supplied by Sirion Therapeutics, as a 5 mL fill in a 6 cc LDPE bottle and is a multidose sterile solution.

5.1.2 Vehicle

The vehicle will be supplied by Sirion Therapeutics in a container-closure system identical to the study drug.

5.2 Treatments Administered

Subjects who meet inclusion criteria at baseline (Day 0) will be randomized to 1 of 3 treatment groups:

Treatment Group 1: Approximately 65 subjects will receive 1 drop of CSA 0.1% per eye 2 times per day (BID) for 90 days

Treatment Group 2: Approximately 65 subjects will receive 1 drop of CSA 0.2% per eye BID for 90 days

Treatment Group 3: Approximately 65 subjects will receive 1 drop of vehicle per eye BID for 90 days

5.3 Selection and Timing of Dose for Each Subject

All subjects will self-administer the allocated treatment. Subjects will be instructed to administer a dose in the morning and a dose in the evening, with approximately 12 hours between doses.

5.4 Method of Assigning Subjects to Treatment Groups

Subjects will be randomly assigned 1:1:1 to receive CSA 0.1%, CSA 0.2%, or vehicle. Randomization will be conducted by assigning each eligible subject a number that corresponds to a block randomization list generated by an independent statistician. The vendor responsible for packaging and shipping the study drug will be responsible for maintaining trial treatment randomization codes. Randomization will be assigned online via electronic data capture software. Emergency codes will be available via a toll-free number manned continuously throughout the trial period.

5.5 Masking

This study is double-masked; all clinical site personnel, the subject, and Sirion Therapeutics personnel will be masked to treatment allocation. The investigational products will be indistinguishable from each other in packaging appearance. The vendor responsible for packaging and shipping the study drug will be responsible for maintaining the randomization codes.

5.5.1 Unmasking During the Study Period

Should it be necessary to unmask a subject's treatment assignment in case of emergency, the Investigator should follow the procedure outlined below. The randomization code is to be obtained only if a medical emergency exists and knowledge of the medication being taken will influence the medical management of the subject. In the event of emergency or life-threatening condition, the Investigator may need to unmask the subject.

The following procedure should be followed:

1. The Investigator should contact Sirion Therapeutics immediately before unmasking a subject unless it is not possible to do so without risk to the subject. If the cannot contact the Medical Monitor and the situation is an emergency, the clinical trial material labeler should be contacted. The contact number can be found on the label of the clinical trial material as well as provided with the clinical trial material shipments.
2. The Investigator should document the adverse event (AE) or serious AE (SAE) and justification for unmasking in the eCRF. This information should be noted in the relevant AE or SAE eCRF form.
3. The subject may continue to participate in the study at the Investigator's discretion. If the subject is withdrawn from study treatment prematurely, all of the measures should be performed as soon as possible following the final dose of study drug providing the subject has not withdrawn consent and recorded on the appropriate eCRF.
4. The Investigator should contact Sirion Therapeutics within 24 hours with the randomization number, subject initials, details of the AE or SAE, any action taken, and whether the subject is continuing in the study.

5.6 Concomitant Medications

Artificial tears (Refresh Plus[®]) will be dispensed to subjects for use during the treatment period. **Subjects will be instructed to use the artificial tears only as needed up to 8 times per day. Subjects also will be instructed not to use the artificial tears within 30 minutes of instilling the study drug.** All other artificial tear products, including any topical ophthalmic medications other than the assigned study medication, must be discontinued from screening through Day 90.

Subjects will be excluded from the trial if they are receiving concurrent systemic cyclosporine. Additionally, systemic and topical ophthalmic medications that are known to

cause dry eye disease are prohibited and must not have been taken within 7 days of screening. These include the following medications:

- Immunomodulators (permitted if dose is stable for 3 months prior to screening and not expected to change during the study period)
- General anesthetics
- Antihistamines (including OTC)
- Cholinergics
- Antimuscarinics
- Tricyclic antidepressants
- Phenothiazines

5.6.1 Prior Therapies

Certain prior therapies will not be allowed:

- Current systemic use of cyclosporine
- Topical CSA 0.05% (Restasis) within 3 months prior to screening.
- Presence of punctal occlusion (permanent or temporary)
- Intraocular or refractive surgery (including cataract extraction, LASIK, vitrectomy, or trabeculectomy) in the study eye within 3 months prior to study start

5.7 Treatment Compliance

Subjects will self-administer the study drug during the treatment period. The importance of compliance with the dosing schedule should be stressed to the subject. Subjects will be asked about their medication administration at the Day 14, 28, 42, 60, and 90 study visits.

5.8 Packaging and Labeling

CSA 0.1%, CSA 0.2%, and vehicle will be packaged in identical bottles. Artificial tears (Refresh Plus) will be provided in the commercial packaging.

5.9 Storage and Accountability

The study drugs should be stored at room temperature, 20°C to 25°C (68°F to 77°F), in the original packaging. The subjects should maintain study medications at room temperature at all times, and return all study medications at the last study visit (Day 90).

Upon receipt of the study drug supplies, an inventory must be conducted as soon as possible. Sites will record the number of bottles received and the number assignment printed on each bottle in the Drug Accountability section of the eCRF. A copy of the drug receipt form must be kept in a secured location at the site. During the trial, the site must account for all investigational drug product additions, usage, discrepancies, or deficiencies on the Drug Accountability section of the eCRF. All supplies must be accounted for at the conclusion of the study; therefore, no used or partially used supplies should be discarded. Subjects should

be requested to return all used or unused study medication. Any accidental or deliberate destruction of the investigational drug products should be documented on the Comments page of the eCRF.

During the study close-out process, the clinical monitor and site personnel will work together to inventory all supplies on a drug-return form. All used and unused study drug products must be returned by a traceable method to the vendor designated by Sirion Therapeutics. A copy of the drug return form must be kept in a secured location at the clinical site.

